II. Informed Consent Form Template

Not applicable - we will request a waiver of consent.

III. Other (*add as many appendices as necessary*)

STUDY TEAM ROSTER

[name]. (Principal Investigator), Leonard D. Schaeffer Center for Health Policy and Economics, University of Southern California, [name], Office: [contact], [contact], [contact]

[name] (Co-Investigator), Scripps Mercy Hospital Emergency Department and San Diego County Rx Drug Abuse Medical Task Force, [contact]

[name] (Co-Investigator), San Diego County Medical Examiner's Office, [name], [contact]

[name]. (Project Manager), Leonard D. Schaeffer Center for Health Policy and Economics, University of Southern California, [name], Office: [contact], [contact], [contact]

[name] MPH (Co-Investigator), Leonard D. Schaeffer Center for Health Policy and Economics, University of Southern California, [name], Office: [contact], [contact], [contact]

PARTICIPATING STUDY SITES

San Diego County Medical Examiner's Office. [name], Chief Deputy Medical Examiner, [name], (PHONE/FAX), [contact]

PRÉCIS.

Study Title: Behavioral insights to encourage judicious prescribing of opioids

Objectives

In collaboration with the San Diego Medical Examiner's Office and the State of California's controlled Substance Utilization Review and Evaluation System (CURES), we propose to review opioid poisonings over the past 12 months and will send letters to prescribers in San Diego County when one of their prescriptions was filled by a patient who died of an opioid poisoning. The letters will be non-judgmental and factual, explaining that a patient of theirs who was being treated with prescription narcotics died of an opioid poisoning. The letter will also encourage judicious prescribing including use of the CURES system before prescribing. We will evaluate physician prescribing practices over 24 months (12 months pre- and 12 months post-letter) using data from the CURES database. Our hypothesis is that letters will make the risk of opioids more cognitively available and that physicians will respond by prescribing them more carefully. This will result in fewer deaths due to misuse and more frequent use of the CURES system.

Design and Outcomes

We will conduct a cluster randomized trial of an informative intervention targeting the over-prescription of scheduled drugs with patient death as the unit of randomization.

The follow outcomes will be analyzed:

- 1) Fewer opioid prescriptions written among clinicians receiving the letter, compared to controls;
- 2) Lower cumulative Morphine Equivalent Dose (cMED) among clinicians receiving the letter (as indicated by dosing on prescriptions filled);
- 3) More frequent use of CURES among clinicians receiving a letter;
- 4) Fewer opioid prescriptions for ≥ 100 milligram morphine equivalent (MME)
- 5) Fewer benzodiazepine co-prescriptions

In the main analysis, we will compare a 12-month baseline period to a 12-month post-treatment follow-up period.

Interventions and Duration

The intervention will be a one-time treatment for all participants, with a three-month and a one year follow-up period to measure the persistence of the effects after the intervention.

The following intervention will be analyzed:

A courtesy communication informing prescribers of the death of a former patient where prescription drug overdose was the primary cause or contributed to the cause of the death. The letter will invite prescribers to review materials regarding the clinical guidelines from the Center of Disease Control, the California Department of Public Health, and the San Diego County Prescription Drug Abuse Medical Task Force for a more prudent prescription of those drugs.

Sample Size and Population

Our sample will consist of a heterogeneous group of clinicians and allied health professionals with scheduled drug prescribing privileges practicing in San Diego County who prescribed a Schedule II-IV drug (i.e., drugs as defined by the United States Controlled Substances Act as having an abuse potential, but also a currently accepted medical use) to a person who died as a result of a Schedule II-IV accidental drug death.

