5.2 Handling of Study Interventions

Letters will be carefully edited by an advisory group to ensure tone is supportive and its recommendations consistent with CDC guidelines. Letters will be generated, signed by the San Diego Medical Examiner and posted in the U.S. mail. The pre-intervention baseline period will be 12 months in length with a one year follow-up period to measure the persistence of effects after the intervention.

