6.1.2 Enrollment, Baseline, and/or Randomization

Enrollment

Participants will not be enrolled; we will intervene on all clinicians and allied health professionals with prescribing privileges and at least one prescription drug death as part of a public health program to encourage safe prescribing in San Diego County. Informed consent of patients and clinicians is waived under HHS regulations at 45 CFR 46.116(c), as the study is evaluating a County public service safe prescribing program.

Baseline Assessments

For the baseline assessment, the study team will evaluate physician prescribing practices in the 12 months pre- intervention using data from the CURES database.

Randomization

For randomization, six decedent lists were generated from the crossed strata levels. Using random.org's sequence generator,(16) true random integer sequences derived from atmospheric noise determined decedent order in each list. For each ordered list, prescribers to decedents in the first half were those who received the intervention.

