9.4 Outcomes

9.4.1 Primary outcome

Our primary analysis assesses changes over time before and after the intervention in natural log-transformed MME between treatment and control.

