9.5 Data Analyses

Descriptive and inferential statistics will be carried out in STATA (Version 14.0; Stata Corporation, College Station, TX). The *cmp* command in STATA will be used to compute a difference-in-differences estimator within a mixed-model censored linear regression.(17) The difference-in-differences estimator compares the average change over time in MME dispensed for prescribers in the intervention group, compared to the average change over time for prescribers in the control group. The natural log transformation of MME ensures normally distributed data. Censored regression has a continuous component and a discrete one. Natural log MME doses estimated over days where opioids were dispensed in the name of a prescriber represent the continuous part, and days with no opioids filled in that prescriber’s name represent the discrete part of the model. We denote estimation of the dependent variable as $\log(\overline{MME})^*$ to distinguish it from uncensored estimation. The analysis is represented by:

$$\log(\overline{MME})^*_{ijk} = \beta_1 x_{1ij} + \beta_2 x_{2ij} + \beta_3 x_{3ij} + \delta_{i(k)} \quad [1]$$

where β_1, β_2 and β_3 are fixed effects coefficients on time, x_1 , intervention, x_2 , and time by intervention interaction, x_3 , respectively. Alphabetic subscripts describe the i th prescriber, j th prescription filled and k th decedent, the nested random intercept $\delta_{i(k)}$ is normally distributed with mean zero and variance, $\sigma_{i(k)}^2$, for each i prescriber nested in (i.e., having prescribed to) decedent $k, i(k)$. With natural log transformed data, the value $100 \cdot [\exp\{\beta_3\} - 1]$ measures the percentage change in MME attributable to the intervention when data are uncensored.(18) However, when data are censored the coefficient β_3 must be adjusted to reflect the effect on the observed outcome. We will evaluate data 3 months pre-intervention and 3 months post-intervention, with

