post-intervention beginning one month after the letter was sent to washout contamination by prescriptions written before receipt of the letter but filled afterwards. For the one-year analysis we will include a regressor to control for the 3-month effect. We will perform sensitivity analysis on regression assumptions. As secondary hypotheses, we evaluate if the intervention cohort had 1) fewer high-dose opioid prescriptions (≥ 50 or > 90 MME per day), or 2) fewer new patients who were started on opioids. High-dose prescriptions will be evaluated using censored regression on percent of clinician fills on high-dose. Chance of a fill being a “new start” will be evaluated using logistic regression. These analyses will also be conducted within a difference-in-differences framework.

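### The window labelled as the main analysis (12 v 12 months) conflicts with the window of the only written log-MME model (3 v 3 months); neither is designated for the 5% test, and the one-year model's extra regressor is uncoded

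*Combined protocol and SAP*

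**What the plan says.** **Window.** The Précis, under Design and Outcomes, states: "In the main analysis, we will compare a 12-month baseline period to a 12-month post-treatment follow-up period". No other window in the document carries that label. The Précis objectives ("We will evaluate physician prescribing practices over 24 months (12 months pre- and 12 months post-letter"), Section 5.2 ("The pre-intervention baseline period will be 12 months in length with a one year follow-up period") and Section 6.1.2 ("the study team will evaluate physician prescribing practices in the 12 months" before the intervention) describe the same yearly scale.

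Section 9.5 gives equation [1], the only written model for log MME, with fixed effects for time, intervention and their interaction (β3). The window attached to it is different: "We will evaluate data 3 months pre-intervention and 3 months post-intervention", with "post-intervention beginning one month after the letter was sent to washout contamination". One year then appears as a further analysis: "For the one-year analysis we will include a regressor to control for the 3-month effect". No equation or coding for that regressor follows.

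Section 9.4.1, where the primary outcome is defined, gives no window: "Our primary analysis assesses changes over time before and after the intervention in natural log-transformed MME between treatment and control". Nor does the primary objective in Section 1.1.

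**Test.** Section 9.2 assumes one two-tailed test with 5% Type I error. Its inputs refer to no pre or post window, and no multiplicity rule is given anywhere.

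**The concern.** A reader looking for the primary test finds two candidates. One has the label, and the other has the written model. As the text stands, either could be presented as the planned 5% test, so the choice could be made after both results are known. The choice matters for the substance as well: if the effect of a single letter fades, the 3-month estimate will be larger than the 12-month one, and persistence is a stated interest of the trial.

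The one-year analysis has its own gap. Adding a term for the first three months can change what β3 estimates. Without the coding, a later-months effect could be reported as the average over the year, or the reverse.

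**Working it through.** **Step 1. The texts side by side.**

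| Place | Window |
|---|---|
| Précis, Design and Outcomes | 12 v 12 months, labelled main |
| Précis, Interventions and Duration | three-month and one-year follow-up, not ranked |
| Section 1.1 | none |
| Section 9.4.1 | none |
| Section 9.5, after equation [1] | 3 v 3 months after a one-month washout |
| Section 9.5, one-year analysis | one year, extra regressor, no equation |
| Section 9.2 | 5% two-tailed, no window |

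The plan gives no figure that depends on the window. The 65 decedents per arm use no pre/post period, so they cannot settle the question.

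**Step 2. What an open choice would cost in Type I error.** Assumptions, not in the plan: success in either window may be claimed at two-sided 5%; 12 post-washout months; independent monthly values of equal variance. The factor for two arms cancels from each correlation, so it is omitted.

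- 3 v 3: variance 1/3 + 1/3 = 2/3.
- 12 v 12: variance 1/12 + 1/12 = 1/6. Covariance with 3 v 3: 1/12 + 1/12 = 1/6. Correlation (1/6)/√(2/3 × 1/6) = 0.50.
- Later 9 months v 12 baseline months: variance 1/9 + 1/12. Covariance with 3 v 3 (shared baseline only): 1/12. Correlation (1/12)/√[(2/3)(1/9 + 1/12)] = 0.23.

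P(|Z1| > 1.96 or |Z2| > 1.96) from the bivariate normal:

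| Correlation | False-positive rate |
|---|---|
| 0.23 (3 v 3 with later months) | 9.6% |
| 0.50 (3 v 3 with 12 v 12) | 9.1% |
| 0.7 (assumed, persistent prescriber changes) | 8.3% |
| 0.8 (assumed) | 7.8% |

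**Step 3. What β3 means in the one-year model.** Illustrative inputs, not from the plan: effect -10% in the first 3 post-washout months (ln 0.90 = -0.1054) and -4% in the next 9 (ln 0.96 = -0.0408); 12 baseline months; an early shift of +0.02 on the log scale common to both arms. The fit is least squares on noise-free, uncensored monthly log means.

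- *No extra regressor, or an early-period term shared by both arms.* β3 is the 12-month average: (3/12)(-0.1054) + (9/12)(-0.0408) = -0.0570, or -5.5%.
- *Early-period main effect plus early-by-intervention term.* β3 is the later-months effect: -0.0408, or -4.0%.
- *Early-by-intervention term alone.* The control arm has no early term, so its post-period mean absorbs (3/12)(0.02) = 0.005 of the shared shift. β3 = -0.0408 - 0.005 = -0.0458, or -4.5%. With the same shift and no true effect, β3 = -0.005, or -0.5%.

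The third coding is the literal single regressor if the 3-month effect is read as an intervention effect. It estimates neither the year average nor the later effect unless there is no early shift common to both arms.

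**The case against.** The strongest reply is that the plan discloses both horizons. The Précis announces a three-month and a one-year follow-up, and describing the one-year period as a measure of persistence (Précis, Sections 3 and 5.2) fits a design with 3 months primary and one year secondary. The Précis sentence with the main-analysis label also follows a list of five outcomes that includes cumulative dose but does not name daily log MME. These points stand. They rule out any inference that a window was concealed, and they mean the document does not establish 12 months as the true primary. They do not resolve the conflict, because no sentence ranks the windows for log MME.

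The error rates rest on an either-window rule that appears nowhere in the plan, and on equal, independent months, whereas equation [1] is indexed by prescription fill. A reader might infer that the trial's Type I error is 9.6%. The document does not support that; the figures show only what an undesignated choice would cost.

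On the one-year model, the shared-term reading is the weaker one, since it leaves β3 exactly where it would be with no extra regressor. The ambiguity is therefore narrower than an even choice between codings, but the more natural reading still has two versions, with and without the early main effect, and they give different answers. Nor is it safe to say that the coding is harmless when the effect is constant: that fails for the interaction term alone whenever both arms share an early shift.

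A reader might also count the 4 months in the Section 6.1 schedule and the 13 months in Sections 6.1.3 and 6.1.4 as further contradictions. They are not: they fit 1 + 3 and 1 + 12. Only the schedule's 12-month column sits awkwardly with the 13 months. Finally, the past tense in Section 9.4.2 might suggest that the analysis is already done, but Section 9.5 repeats the same sentences in the future tense, so the wording does not show it.

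**Conclusion.** The point holds as a failure of designation. The labelled main window (12 v 12) and the window of the only written log-MME model (3 v 3 after washout) disagree, and neither is assigned the two-tailed 5% test. This follows from the text alone and needs no assumption. If either window could be claimed, the false-positive rate would be about 8% (correlation 0.7 to 0.8) to 9.6% (independent, equal-variance months).

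The one-year model is under-specified. On the illustrative effects, β3 is -5.5%, -4.0% or -4.5% according to coding, and the single-interaction coding can be biased even under no effect. The sizes depend on the assumed effects and shift; that the coding determines what β3 estimates does not. This should be fixed before the result is interpreted, because it decides which number is the trial's primary finding.

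**What to change.** 1. In Section 9.4.1, name one primary window for log MME, tested at 5% two-sided: 12 months, as the Précis labels it, or 3 months if the sponsor intends that. Make the Précis and Section 9.5 agree, and label the other window secondary.
2. Do this before outcome data are analysed. If they have already been analysed, report both windows and disclose that the plan was inconsistent.
3. If 12 months is primary, test β3 of equation [1] fitted to the 12 v 12 data without the extra regressor.
4. For the persistence analysis, write out the model with both an early-period main effect and an early-period-by-intervention term. Report β3 as the later-months effect, not as the average over the year.
5. State that the one-month washout also applies to the one-year window, and align the 12-month column of the Section 6.1 schedule with the 13 months in Section 6.1.3.

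The cost is wording and one equation, with no new data. The sponsor gives up a second chance at a primary claim.

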1. STUDY OBJECTIVES

1.1 Primary Objective

Our primary objective is to analyze prescribers in the treatment group's milligram morphine equivalent dose (mg MED) compared to the control participants before and after the intervention.

1.2 Secondary Objectives

Our secondary objective is to observe frequency of CURES use and the number of "new starts".

2. BACKGROUND AND RATIONALE

2.1 Background on Condition, Disease, or Other Primary Study Focus

Much of the increase in opioid prescribing rates from 1999 until the past decade has been driven by an increase in the use of prescription opioids to treat non-cancer pain ([Guy et al. 2017](#); [Boudreau et al. 2009](#)). Although opioids carry significant risks of overdose and addiction, they are no more effective for treating chronic non-cancerous pain over a one year period than non-opioid alternatives ([Krebs et al. 2018](#)). The greater availability of prescription opioids has been accompanied by an alarming rise in the negative consequences related to opioid use. In 2017, there were 17,029 prescription opioid overdose deaths in the US ([Scholl 2019](#)). The costs of prescription opioid adverse outcomes are staggering. Aggregate costs for prescription opioid harms are estimated at over \$78.5 billion (in 2013 USD) and 25% of the aggregate economic burden is publicly funded (i.e., Medicaid, Medicare, and veterans' programs) ([Florence et al. 2016](#)).

In 2016, the Centers for Disease Control and Prevention (CDC) issued the "CDC Guideline for Prescribing Opioids for Chronic Pain" which encourages the use of alternatives to opioids and other practices that minimize harm to patients ([Dowell et al. 2016](#)). Despite the introduction of this guideline, primary care clinicians, who prescribe 45% of all opioid prescriptions in the US, report challenges in following these recommendations ([Kroenke et al. 2019](#)). The dynamics of opioid use make following guidelines difficult. Since opioid analgesia from a given dose declines with chronic use due to opioid tolerance, doses increase and the chance of harm grows. Over time, the primary benefit of opioids for many patients becomes the avoidance of withdrawal. As patients become dependent on opioids, they may misconstrue the treatment of interdose withdrawal hyperalgesia as ongoing effectiveness and they may become reluctant to stop opioids

[\(Juurlink 2017\)](#). More cautious opioid prescribing (including fewer new starts, avoidance of high doses, and slow, collaborative tapers for those already on high dose long-term therapy) can improve the balance of benefits and harms for patients with chronic pain. To embrace more cautious prescribing, a clinician may need to be informed that opioid risks are present and relevant to his/her own patients.

2.2 Study Rationale

Prescriber's invited to join efforts to exercise more careful use of opioids may be more likely to do so after they have been made aware of an opioid death in their practice. They may also be more likely to dedicate themselves to amending their prescribing practices, committing to become an "aide in practice" and identify careful use of opioids with their self-image in the future. Many physicians underestimate the risk of opioids in their own practice, and currently, there is no mechanism for medical examiners to identify prescribing physicians, nor for physicians to be alerted about deaths, despite substantial interest from the CDC on solving this problem. One promising strategy for changing physician behavior is through use of "nudges". The term "nudge" identifies a set of social and cognitive devices that persuade decisions in subtle ways while preserving choice. When prescribing narcotics, physicians may not have recent experiences that come to mind as to why these drugs are dangerous, making risks seem remote. They may also not consult data on a patient's other narcotic prescriptions in their State's pharmaceutical drug monitoring program. One useful nudge capitalizes on a finding called "Availability". Availability is the notion that people rely upon knowledge that is salient, recent and readily available to them to evaluate risks and make decisions. If a physician issued a prescription for a narcotic that resulted in a recent opioid poisoning, providing that physician with this feedback may make the physician more likely to consult a pharmaceutical drug monitoring program database and also prescribe more judiciously.

3. STUDY DESIGN

The trial is a cluster-randomized controlled trial with prescriber as the unit of randomization. The primary aim is to test the ability of the informative intervention to reduce the number of Scheduled drug prescriptions. We will randomize prescribers in a 1:1 design where half will be in the control group while the other half receives the intervention. All physicians involved in prescription drug over-dosage related deaths in the 12-month baseline period will be randomized to receive a letter regarding that death as well as guidelines for future consideration regarding prescribing practices. The intervention will be followed by a one year follow-up period to measure persistence of effects. Data from the Controlled Substance Utilization Review and Evaluation System 2.0, which is California's prescription drug monitoring program, will be extracted and transferred to the Data Coordinating Center on a weekly basis.

4. SELECTION AND ENROLLMENT OF PARTICIPANTS

4.1 Inclusion Criteria

The subjects involved in this trial are clinicians will be from those who prescribe Scheduled drugs and practice in the County of San Diego. Clinicians must meet the following inclusion criteria to be selected to participate in the study: 1) have given at least one prescription for any sort of opioid medication to patients and 2) prescribed to a patient who have deceased within the 12-month baseline period where prescription drug overdose was the primary cause or contributed to the cause of death.

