4.3 Study Enrollment Procedures

Participants will not be enrolled; we will intervene on all clinicians and allied health professionals with prescribing privileges and at least one prescription drug death as part of a public health program to encourage safe prescribing in San Diego County. Informed consent of patients and clinicians is waived under HHS regulations at 45 CFR 46.116(c), as the study is evaluating a County public service safe prescribing program. Deaths where prescription drugs are the primary or contributing cause will be cataloged by the medical examiner between the period of July 1st, 2015 and June 30th, 2016. As part of the County safe prescribing program, prescribers to those deaths are identified in the CURES system. All California pharmacies and clinics that dispense controlled substances must submit reports to CURES on a weekly basis. In consultation with the program manager of CURES, a letter notifying CURES administrators that prescriptions from these clinicians would be evaluated prospectively after the safe prescribing letters were sent was submitted to the CURES system.

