7. SAFETY ASSESSMENTS

7.1 Specification of Safety Parameters

Although we will be unable to determine if there are hospitalizations or ED visits for opioid withdrawal in patients of clinicians in the intervention group, we will monitor this potential safety issue by comparing clinicians who received a letter to controls to determine if there are any dramatic reductions (>20% from baseline) in opioid prescribing in the post-intervention period as a result of the letter. The U.S. does not have an integrated healthcare system with complete data on hospitalizations for all patients to evaluate induced withdrawal. However, it is possible for us to evaluate if providers induce withdrawal in patients by exhibiting high rates of MME reductions.

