10. DATA COLLECTION AND QUALITY ASSURANCE

10.1 Data Collection Forms

The Controlled Substance Utilization Review and Evaluation System (CURES) will provide records of opioids dispensed at California pharmacies attributable to each provider in our sample treating all civilian, non-Veteran’s Administration and non-institutionalized patients. CURES is California’s prescription drug monitoring program. The Medical Examiner has authority to use CURES for the purpose of educating practitioners and others in lieu of disciplinary, civil, or criminal actions, in accordance with the California State’s Health and Safety Code § 11165(c)(2). First name, last name, date of birth and address identified each decedent in the medical examiner reports and CURES data. Drug Enforcement Agency (DEA) number identified the prescribers in CURES data. Data from eligible clinicians will be extracted from CURES and kept onsite at the medical examiner’s office for de-identified analytic file preparation. A file stripped of patient and clinician identifiers will be prepared and released for analysis on secure servers at the University of Southern California.

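### Index decedents' own fills are not removed from the outcome data: they add avoidable noise, not bias, to the arm contrast, and let a death count toward the >20% safety reduction

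*Combined protocol and SAP*

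**What the plan says.** - **Eligibility (4.1).** A clinician enters by having "prescribed to a patient who have deceased within the 12-month baseline period". Section 4.3 dates the catalogued deaths "between the period of July 1st, 2015 and June 30th, 2016". Sections 5.2 and 6.1.2 make the baseline the 12 months before the intervention. The date of the letter is not given.
- **Data (10.1).** The CURES extract covers opioids "attributable to each provider in our sample treating all civilian", non-VA and non-institutionalised patients. No section excludes the decedents.
- **Windows.** The Précis says "In the main analysis, we will compare a 12-month baseline period to a 12-month post-treatment follow-up period". Section 9.5 says "We will evaluate data 3 months pre-intervention and 3 months post-intervention, with" the post period "post-intervention beginning one month after the letter was sent to washout contamination", and adds a one-year analysis.
- **Model (9.5).** The test is the time-by-intervention coefficient in a censored mixed model of log MME. The only random effect is an intercept for prescriber nested in decedent.
- **Randomisation (9.1, 9.2.1).** Decedent clusters are split in half within six strata: single or multiple deaths, crossed with opioid, combined or benzodiazepine-only cause.
- **Safety (7.1, 7.6).** Letter recipients are compared with controls for "any dramatic reductions (>20% from baseline) in opioid prescribing", read as a sign of possible induced withdrawal. Section 7.3 adds a chart review of every case that a safety measure identifies.

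**The concern.** A patient who died before the letter can contribute fills only to the pre period. A prescriber who supplied that patient with listed opioids therefore shows a fall that is unrelated to the letter or to any prescribing decision. Two things are at stake.

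1. **Precision, and possibly the standard error.** The size of the fall varies with the date of death, the decedent's volume with that prescriber and the size of the prescriber's panel. The date of death is common to all prescribers in a randomised cluster, so part of this variation is shared within the unit of randomisation. A random intercept describes shared level, not shared change.
2. **Meaning of the safety measure.** A reduction caused by a death is indistinguishable from one caused by a rapid taper. Balance between arms does not help when individual cases are reviewed.

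**Working it through.** **The plan's own figure.** The one related figure is 65 decedents per arm (9.2). It cannot be reproduced, because the baseline mean that would turn a 5% difference into MME is not stated. It is used below only as the number of clusters, with the plan's mean cluster size of 4.5 and coefficient of variation of 1.22.

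**Step 1. How much of the pre window the decedents occupy.** Assume deaths uniform over the 12-month death period.

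| Letter sent | 12-month window | 3-month window |
|---|---|---|
| At end of death period | 0.50 | 0.25 × 0.5 = 0.125 |
| 3 months later | 0.75 × 4.5/12 = 0.28 | 0 |
| 12 months later | 0 | 0 |

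Sections 4.1, 4.3 and 5.2 read together point to the first row, but no section states the date. In the 3-month window, even with no lag, 9/12 = 75% of decedents died before it opened and contribute nothing.

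**Step 2. Size of the fall for one prescriber.** Let N be the number of opioid patients including the decedent, the others at average dose for the whole window. Let f be the fraction of the window the decedent was alive, and d the decedent's volume with this prescriber relative to an average patient. The fall in total MME is df / (N − 1 + df). N and d are assumptions, because the documents give neither.

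- N = 3, d = 1, f = 0.5: 0.5/2.5 = 20%
- N = 10, d = 1, f = 0.5: 0.5/9.5 = 5.3%
- N = 20, d = 3, f = 0.5: 1.5/20.5 = 7.3%
- N = 10, one average patient's volume split equally over 4.5 prescribers (d = 1/4.5), f = 0.5: 0.111/9.111 = 1.2%
- No listed opioid from this prescriber (d = 0): 0%

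**Step 3. Effect on the arm contrast.** A null simulation used 65 clusters per arm, deaths uniform, a 12-month window and no letter lag. The decedent's MME relative to the rest of the panel was set at 0.5% to 30%, with a dose multiplier fully shared within the cluster (an upper-end assumption). The mean difference-in-differences was zero within Monte Carlo error throughout.

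| Decedent's relative share | SD of contrast (noise SD 0.2) | Type I error, noise SD 0.2 / 0.5 |
|---|---|---|
| Fills removed | 0.016 | 0.053 / 0.048 |
| 2% | 0.017 | 0.059 / 0.050 |
| 10% | 0.022 | 0.122 / 0.064 |
| 30% | 0.039 | 0.323 / 0.131 |

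The type I error is for a prescriber-level t-test with no shared-change term, a simplified stand-in for equation [1]. A cluster-robust test held 0.054 to 0.060 with no fills removed.

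With panel sizes drawn at random instead, the ratio of the contrast's variance with and without decedent fills was:

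| Assumption | Median panel 50 | Median panel 20 |
|---|---|---|
| 12 months, decedent a full patient of each prescriber | 1.04–1.68 | 1.17–3.3 |
| 12 months, volume split equally over the cluster | 1.00–1.11 | 1.03–1.50 |

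With the volume split and a 3-month window the range was 1.00–1.10. With a 3-month window and a 3-month letter lag it was exactly 1.00. The upper ends move with how the smallest panels are handled: repeat runs gave 1.46 to 1.81 for median 50 and 2.61 to 3.67 for median 20.

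**Step 4. Effect on the >20% measure.** Take it as judged per prescriber on total MME over 12 months. The decedent's loss alone exceeds 20% when df > 0.25(N − 1). Since f is at most 1, that needs N ≤ 4 at d = 1, or N ≤ 12 at d = 3. In larger panels the loss only adds to ordinary variation. If the log change has SD τ, the chance of a flag is Φ{[ln 0.8 − ln(1 − fall)]/τ}:

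| Fall | τ = 0.2 | τ = 0.4 |
|---|---|---|
| 0 | 13% | 29% |
| 1.2% | 15% | 30% |
| 5.3% | 20% | 34% |
| 20% | 50% | 50% |

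**The case against.** **A tempting stronger reading.** A reader might infer that the fall enters the tested effect, or that a 5% fall rivals the 5% difference assumed in 9.2. The documents do not support either. Controls are also prescribers to decedents, clusters are split in half within strata, and the time coefficient absorbs the common fall. Only chance imbalance in the size of the loss reaches the interaction. A fall within one arm is not on the same footing as a difference between arms.

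**The window.** Section 9.5 works with 3 months before and after. That window holds few of these fills, and none if the letter went out three months or more after 30 June 2016. This stands, and it is why the effect may be zero there. It does not clear the 12-month comparison that the Précis calls the main analysis, or the one-year analysis in 9.5. A lag long enough to empty the 12-month window would contradict 4.1.

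**The loss is not uniform within a cluster.** Each prescriber wrote separately, any Schedule II–IV drug qualifies (Précis), benzodiazepine-only deaths are a stratum, and tramadol and buprenorphine are off the opioid list (Section 15). Some prescribers lose nothing. This stands: the noise is partly shared, not common to the whole cluster. Stratification may also balance part of the loss, and the simulations ignore it.

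**The outcome modelled.** The calculations use each prescriber's change in log MME, not the censored fill- or day-level model. If the outcome is dose per fill, losing an average-dose patient leaves the mean unchanged. This also stands, so the variance and error figures are illustrative only.

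**Safety.** The planned comparison is between arms, where equal inflation largely cancels, and many prescribers would be flagged anyway. That answers the comparison, but not the case review in 7.3, which acts on individual flags.

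**Another remedy.** Decedent-cluster-robust variance protects the error rate without removing fills. It does not recover precision or change what a safety flag means.

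**Conclusion.** The point holds as a matter of noise and of interpretation, not bias. The plan leaves the index decedents' fills in the data, and wherever the pre window overlaps the death period they are lost by construction. For the primary contrast the cost ranges from none (3-month window with a letter lag of three months or more, or prescribers with no counted opioid fills to the decedent) to substantial (12-month window, small panels, decedent a full patient of each prescriber). Shares up to about 2% make little difference. The documents do not give panel sizes, decedent volumes or the letter date, so no single figure can be defended.

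The safety consequence is firmer, since it needs only a small panel and a 12-month baseline. It assumes that the >20% reduction is judged per prescriber, which 7.1 and 7.6 do not say outright but the case review in 7.3 suggests. The change is worth making because it is almost free, rests on facts fixed before randomisation and applies identically to both arms.

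**What to change.** Add to 9.5 and to 7.1/7.6: *All fills dispensed to any index decedent are removed from the pre and post windows, in both arms, for the MME, high-dose and safety measures.* It should say any index decedent because a prescriber with several deaths is assigned to only one of them (9.1), and the others' fills would otherwise remain.

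The filter belongs at the Medical Examiner's office, before de-identification. That office already matches decedents in CURES by name, birth date and address, and analysts receive a file without identifiers (10.1), so they may be unable to apply it later. Report the unfiltered version as a sensitivity analysis.

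In the same edit, state the letter date and reconcile the 3-month and 12-month main windows, since these decide how much the filter matters. A decedent-cluster-robust variance or a decedent-by-time random effect would address any shared change that remains.

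Cost: one extra data-preparation step, a sentence in each section and slightly fewer baseline fills. No new data are needed.
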